BAX expression reflects earlier signaling of apoptosis and, thus, it is a more sensitive biomarker of apoptosis than TUNEL. Necroptosis is a new pathway for programming cell death. Cell proliferation/BAX ratio will be used as a primary endpoint and cell proliferation/TUNEL ratio and cell proliferation/necroptosis ratio will be secondary endpoints.

In contrast to apoptosis, which does not induce inflammation⁴⁹, necroptosis, a programmed necrosis pathway discovered over the past decade^{49,50}, elicits robust adaptive immune responses by inducing the inflammatory response cascade and releasing damage-associated molecular patterns against bacterial infection^{51,52}. In a recent longitudinal study, we found necroptosis and inflammation plays a key role in colorectal carcinogenesis. Composite index scores of necroptosis (e.g. Transient receptor potential melastatin 7 (TRPM7)) with inflammation (i.e. COX-2) or apoptosis (i.e. BAX) can improve the prediction of metachronous polyp/adenoma risk. Increased COX-2 intensity in the epithelium was seen during carcinogenesis (Ptrend=0.02) and was significantly associated with an increased risk of metachronous polyp (OR=5.12, 95% CI: 1.50-17.45, Ptrend=0.008), and for both metachronous adenoma/serrated polyp. Higher expression of TRPM7 was marginally associated with risk of

metachronous adenoma/serrated polyp in a dose-response manner. Combined composite index scores of necroptosis with inflammation or apoptosis using principal component analysis were strongly associated with a 4- to 17-fold increased risk of metachronous adenoma/serrated polyp. We have presented the results in 2022 AACR Annual Meeting. The manuscript will be submitted for publication shortly. Therefore, we propose to add 1) COX-2 expression in rectal biopsy; 2) BAX in rectal biopsies; 3) TRPM7 in rectal biopsies; 4) joint index of COX-2 with TRPM7 expression in rectal biopsies; and 5) joint index of TRPM7 with BAX in rectal biopsies as exploratory endpoints.

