8.2 Secondary and Exploratory Endpoints

Immunohistochemistry (IHC)

Cell proliferation/TUNEL ratio, and cell proliferation/Necroptosis ratio will be secondary endpoints, whereas the expression of COX-2, BAX, TRPM7, joint index of COX-2 with TRPM7 and joint index of TRPM7 with BAX in rectal biopsy will be exploratory endpoints.

All biomarkers (TUNEL, pMLKL, COX-2, BAX, TRPM7 and Ki-67) will be detected by an established 6-plex mIHC/IF (multiplex immunofluorescent IHC) technique and analyzed quantitatively using a system composed of an Olympus BX-61 motorized microscope, X-Cite XYLIS Fluorescence Illuminator and imaging software (Q-Capture, ImageJ, CellProfiler). The imaging quantification will be conducted by a research pathologist and the detailed procedures for sequential mIHC/IF staining protocol, quality controls and automated image measurement pipelines are presented in the supplementary file. The final measures are generated automatically as “total positive cell count / total epithelial nuclei” for nuclear staining marker (Ki-67), or “total positive area / total epithelial cell area” for cytoplasmic/membranous staining markers (i.e. pMLKL, TRPM7, COX-2 and BAX). The COX-2 expression in both epithelium and stroma will be separately quantified using pan-CK for tissue segmentation. Quantitative results will be used for endpoints and semi-quantitative results will be used to validate quantitative results.

Fecal occult blood test

Fecal occult blood test will be used to monitor the safety of the treatment at each clinic visit.

Quantification of DNA methylation

Epigenetics, particularly aberrant DNA methylation in gene promoters (i.e. CpG methylation sites), play a critical role during CRC carcinogenesis^{55,56}. However, a very recent human study found that use of aspirin reduced the CpG methylation rates at colorectal carcinogenic genes (i.e. CDKN2A (cell cycle regulation), MGMT (DNA repair), DAPK1(apoptosis), CDH1(cell invasion), WNT16 (Wnt pathway) and RASSF1 (RAS signaling))⁵⁷.

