13.5 Secondary and Exploratory Objectives, Endpoints, Analysis Plans

The secondary objectives are to evaluate the effects of aspirin treatments on:

- 1) the ratio of cell proliferation (Ki-67)/apoptosis (TUNEL) in rectal biopsies
- 2) the ratio of cell proliferation (Ki-67)/necroptosis (pMLKL) in rectal biopsies
- 3) fecal occult blood test (measures of adverse events) as measured by stool samples

The exploratory objectives are to evaluate the effects of aspirin treatments on:

- 1) COX-2 in rectal biopsies
- 2) BAX in rectal biopsies
- 3) TRPM7 in rectal biopsies
- 4) joint index of COX-2 with TRPM7 expression in rectal biopsies;
- 5) joint index of TRPM7 with BAX in rectal biopsies;
- 6) methylation assays using the MethylationEPIC BeadChip to identify methylation biomarkers in genes (i.e. CDKN2A (cell cycle regulation), MGMT (DNA repair), DAPK1(apoptosis), CDH1(cell invasion), WNT16 (Wnt pathway) and RASSF1 (RAS signaling)) involved in colorectal carcinogenesis, and other epigenome-wide methylation biomarkers as measured in rectal biopsies;
- 7) metagenomics analysis to measure abundance of *E. coli* and *Fusobacterium* and other microbiota in rectal swabs

The majority of secondary and exploratory endpoints are continuous. Biomarker levels at baseline, 9 and 12 weeks, as well as the corresponding changes from baseline, will be summarized using descriptive statistics including means and standard deviations or medians and interquartile range, as well as graphical methods such as “spaghetti plots” that depict change patterns over time. Distributions of each marker will be examined, and values may be transformed as needed to stabilize the variance or satisfy the normality assumption. Correlation between biomarkers, and between pre- and post-treatment values will be examined using scatterplots with overlayed smoother plots for ease of visual interpretation.

If the normality assumptions are satisfied, paired t-tests will be used to examine whether the biomarkers change from baseline to 12 weeks post-treatment in each treatment arm. Signed rank test will be used if no suitable transformation can be found. Because we expect that the continuous and intermittent dosing regimens will result in similar biomarker changes, we will use the TOST procedure, similar to the primary

endpoint, to test for equivalence. The equivalence margin will be set as 3/4 of the observed standard deviation of the marker at baseline, similar to the primary endpoint.

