Additional analyses will be conducted using linear mixed effects models with repeated measures to further explore biomarker change patterns over time across 3 time points, and to compare them between arms. These models use all available observations accommodating data that are missing at random, rather than performing a complete case analysis.

A placebo arm is included in the secondary analyses because the variations on repeated measurement of the new biomarkers of methylation and microbiota are not known from the previous trials, and therefore changes in the treatment arms are difficult to interpret. The placebo arm is used as a reference for background, as a cohort for analysis.

Fecal occult blood tests will be categorized as binary (present vs. absent) at each time visit. Proportion of patients with at least one positive test will be compared between arms using Fishers exact test because incidence of this adverse event is expected to be low.

Exploratory endpoints of joint index of COX-2 with TRPM7 and joint index of TRPM7 with BAX in rectal biopsies will be analyzed similarly. Indices will be calculated using a scoring approach based on factor analysis.

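### Factor analysis does not define the two-marker TRPM7-BAX index in Section 13.5 (exploratory), and it is not the method behind the association cited in Section 2.3

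*Combined protocol and SAP*

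**What the plan says.** Section 13.5 lists two composite exploratory endpoints, the "joint index of COX-2 with TRPM7 expression in rectal biopsies" and the "joint index of TRPM7 with BAX in rectal biopsies". Its only statement on how they are built is "Indices will be calculated using a scoring approach based on factor analysis". It gives no number of factors, extraction method, constraint, type of score, source of the weights or direction. The indices are to be analysed in the same way as the other markers. For continuous markers that includes the two one-sided tests, with a margin of 3/4 of the observed baseline standard deviation.

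Section 8.2 gives TRPM7 and BAX one quantitative measure each, a positive-area fraction. COX-2 differs: "The COX-2 expression in both epithelium and stroma will be separately quantified using pan-CK for tissue segmentation". Section 13.5 does not say whether one or both COX-2 measures enter the index.

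Section 2.3 gives the reason for these endpoints: "Combined composite index scores of necroptosis with inflammation or apoptosis using principal component analysis were strongly associated" with a 4- to 17-fold increase in the risk of metachronous adenoma or serrated polyp. It then proposes the joint indices on that basis.

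**The concern.** An index is an endpoint only if its formula is settled. Factor analysis separates what indicators share from what is unique to each, and with two indicators there is too little information to do so. Two analysts following Section 13.5 faithfully could produce different TRPM7-BAX scores from the same data, each fitting perfectly, and nothing in the data would favour either.

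Two things are at stake. The equivalence conclusion for the index can depend on a software default. And the trial's index may not be the kind of score behind the risk association in Section 2.3, so a difference or similarity between arms could not readily be read against that association.

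**Working it through.** The plan states no figure for the indices, so there is none to reproduce.

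**Inputs.** Two indicators for TRPM7-BAX (Sections 8.2 and 13.5). Two or three for COX-2-TRPM7, depending on how COX-2 enters (Section 8.2). The TRPM7-BAX correlation r is not given; Section 13.5 says only that correlations between markers will be examined graphically. I assume r from 0.2 to 0.7 and use 0.3 for illustration. The identification result does not depend on r.

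**Step 1: parameter count.** With p indicators, one factor and factor variance fixed at 1, there are p(p+1)/2 variances and covariances, and 2p free parameters (p loadings, p unique variances).

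| p | Moments | Parameters | df |
|---|---|---|---|
| 2 | 3 | 4 | -1 |
| 3 | 6 | 6 | 0 |

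For p = 2 the Jacobian of the moments has rank 3 against 4 parameters: not identified. For p = 3 the model is just identified.

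**Step 2: the set of exact solutions.** For standardised markers with correlation r, any first loading a between r and 1, with second loading b = r/a and unique variances 1 - a² and 1 - b², reproduces the correlation matrix exactly. The regression-score weights are w1 = (a - r·b)/(1 - r²) and w2 = (b - r·a)/(1 - r²). At r = 0.3:

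| Loadings (a, b) | Score weights |
|---|---|
| (0.3, 1.0) | (0, 1) |
| (0.548, 0.548) | (0.421, 0.421) |
| (1.0, 0.3) | (1, 0) |

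The scores at the two ends correlate only r with each other: 0.2, 0.3, 0.5 and 0.7 for those assumed values.

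**Step 3: what routines return.** Principal-axis extraction on standardised markers is symmetric and gives equal loadings: 0.548 each at r = 0.3 and 0.632 each at r = 0.4. A maximum-likelihood run at r = 0.4 gave 0.637 and 0.628, whose product is 0.400: another point on the same exact-fit set. Likelihood fits at r = 0.3 from different start values or marker scales all fitted exactly, with score weights from about (0.42, 0.42) to (0.01, 0.98).

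**Step 4: comparison with principal components.** For two standardised, positively correlated markers the first component has weights (0.707, 0.707) whatever r is, and explains (1 + r)/2 of the variance: 60% at r = 0.2, 65% at 0.3, 75% at 0.5, 85% at 0.7. A factor score constrained to equal loadings correlates 1.000 with it. Other members of the exact-fit set do not: at r = 0.3, a single-marker score correlates 0.806 with the equal-weight score. If r is negative, the first component becomes a difference of the two markers.

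**Step 5: effect on the equivalence test.** Suppose r = 0.3 and the arms differ by 1 SD in TRPM7 and 0 in BAX. In index SD units, the difference is 0 if the score is BAX alone, 1/sqrt(1 + 1 + 2 × 0.3) = 1/sqrt(2.6) = 0.62 with equal weights, and 1.0 if it is TRPM7 alone. The margin is 0.75. The same marker data can therefore lie inside or outside it according to a constraint the plan does not state. The two ends are limits, not forecasts.

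**The case against.** The best reply is that the wording is loose: an approach based on factor analysis could mean principal-component extraction or equal loadings, either of which gives a defined score. With principal-axis extraction on standardised, positively correlated markers, the score coincides with the first principal component. That stands. It shows that a sensible analyst may reach a sensible index, but not that the text requires it, since likelihood extraction is equally within the wording.

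It is also true that these are two of seven exploratory objectives, and that COX-2, BAX and TRPM7 are each analysed separately, so little information is lost.

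Some stronger readings are tempting but unsupported:

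- A reader might infer that the index will in practice collapse to BAX alone or TRPM7 alone. Those are the ends of the mathematical range; common routines often land at or near equal weights.
- A reader might infer that weights will be re-estimated on trial data. Section 13.5 is silent on their source.
- A reader might infer that a validated index is being abandoned. Section 2.3 reports an association from a study not yet published and claims no validation; it also names TRPM7 only as an example of the necroptosis component.
- A reader might worry that a refitted principal component would change sign by chance. The plan names no such refit, and any probability would rest on a correlation the documents do not give.

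**Conclusion.** The point holds in a limited form. The method named in Section 13.5 does not by itself define the TRPM7-BAX index: df = -1, whatever the marker correlation. The COX-2-TRPM7 index shares the defect if one COX-2 measure is used and is just identified if both compartments enter; the plan does not say which. The named method also differs from the principal components in Section 2.3, with no reason given.

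The practical size depends on the routine used. It is nil with principal-axis extraction on standardised, positively correlated markers. It is potentially large with likelihood extraction, where weights from about (0.42, 0.42) to (0.01, 0.98) fitted equally well at the assumed r = 0.3. The primary endpoint, the sample size and the efficacy and safety conclusions are not affected.

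**What to change.** Replace the scoring sentence in Section 13.5 with a fixed-weight definition along these lines:

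*Each joint index is a weighted sum of its markers, with the same weights and scaling at every visit and in every arm. The weights, means and SDs are those of the principal-component score in the earlier longitudinal study (Section 2.3), if they are available and transportable to the present assay. Otherwise the index is the equal-weight sum of z-scores standardised to the pooled baseline mean and SD. The sign of each marker is fixed in advance from the earlier study's loadings or risk direction, not from the trial data. The COX-2 measure entering the index (epithelial, stromal or both) is [to be stated].*

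The fallback is needed because the documents do not contain the earlier loadings, and because Section 2.3 reports COX-2 intensity while Section 8.2 measures positive area. The sign must be stated because Section 2.3 treats more apoptosis as protective but reports higher TRPM7 expression as marginally associated with risk; adding TRPM7 and BAX with the same sign could cancel opposing signals.

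The change is one short paragraph in the analysis plan, made before the index data are seen. It needs no new data and places no burden on participants. The only work is to retrieve the earlier loadings and scaling and judge whether they carry over.

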13.6 Reporting and Exclusions

To impute missing data we will use Multiple Imputation via a Semi-Parametric Probability Integral Transformation. This is an approach for imputing continuous, binary, and mixed data by first mapping these data to normally distributed values and then applying multiple imputation so that distributional assumptions for the original data can be relaxed. This method was developed by [name], of Northwestern University, in 2012.

http://indigo.uic.edu/bitstream/handle/10027/8652/[name].pdf?sequence=1

13.7 Evaluation of Toxicity

All participants will be evaluable for toxicity from the time of their first dose of aspirin.

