5.6 Dose Modification

Individuals who report any GI symptom \geq grade 3, such as dyspepsia or heartburn, will be instructed to discontinue the study medication immediately.

Participants reporting minor upper GI symptoms (dyspepsia or heartburn \leq grade 2) who wish to remain on trial will be instructed to treat symptoms with over-the-counter calcium carbonate and/or magnesium hydroxide based antacids (i.e. Tums®, Rolaids®, Mylanta®, etc.) at the manufacturers recommended dose. If symptoms persist or worsen over the next 3 days while taking antacids (\leq grade 2) and the subject still wishes to remain on trial, they will be instructed to treat symptoms with an over-the-counter proton pump inhibitor (PPI). If symptoms persist or worsen while taking a PPI for more than 3 days then the study agent will be discontinued and the participant will be monitored until symptoms resolve. These symptomatic rescue medications will not be provided to the participants by the study.

Individuals who report the following serious side effects that are possibly, probably, or definitely related to the study agent will be withdrawn from the study:

- Bruising grade 2 or above
- Hearing impairment of any grade
- Tinnitus of any grade
- Nausea grade 2 or worse, or nausea grade 1 that lasts for >5 days

- Vomiting grade 2 or worse, or vomiting grade 1 that lasts for >5 days
- Urine output decrease grade 1 or above
- Urine discoloration grade 1,
- Black/tarry stool,
- Blurred vision grade 1 or above
- Headache grade 3 or above
- Serious allergic reaction to the study agent

Individuals who have one of the following results during the intervention will have the result evaluated immediately (preferably within 1 week) and repeated if the treating physician deems necessary. If the treating physician believes the result is possibly, probably, or definitely related to the study agent, or if the repeated test result remains the same, the individual will be withdrawn from the study.

- Blood hemoglobin<12.0 g/dL (anemia, grade 1)
- Platelet count<150,000/microliter (platelet count decreased, grade 1)
- Aspartate aminotransferase (AST) or alanine aminotransferase (ALT) >1.5 times upper limit of normal (ULN) (AST/ALT increased, grade 1)
- Alkaline phosphatase >1.5 times ULN (alkaline phosphatase increased, grade 1)
- Bilirubin > 1.5 times ULN (blood bilirubin increased, grade 2)
- BUN >40 mg/dL
- eGFR<45 mL/min (chronic kidney failure, grade 2)
- Positive fecal occult blood test

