7. CLINICAL EVALUATIONS AND PROCEDURES

7.1 Schedule of Events

	Clinic Visit 1: Screening	Clinic Visit 2: Baseline, within 6 weeks of Clinic Visit 1	Between-Visit Telephone or Email Contacts	Clinic Visit 3: 9 weeks after start of study agent [6]	Clinic Visit 4: 12 weeks after start of study agent [7]; or Off-Agent Visit [8]
Informed Consent	X				
Eligibility	X				
Registration/Randomization [1]	X				
Collect/Review Questionnaires [2]		X			
Medical History	X				
Physical [13]	X				
Vital Signs [12], Body Measurements [3]	X	X		X	X
Con Med Review	X	X		X	X
Assess Adverse Events	X	X		X	X
Pregnancy Test	X				
Blood Sample for Clinical Labs [10]	X	X		X	X
Blood Sample for Research [11]	X	X		X	X
Urine Sample [9]	X	X		X	X
Stool Sample	X	X		X	X
Rectal Swab		X		X	X
Rectal Biopsies [4]		X		X	X
Dispense Study Agent		X		X	
Collect/Count Unused Pills and Review Participant Diary				X	X
Telephone or Email Contact [5]			X		X [14]
Compensation	X				X

[1] Registration and randomization will occur between Clinic Visit 1 and Clinic Visit 2

[2] Clinic Visit 2: Food Frequency Questionnaire and Baseline Clinic Visit Questionnaire

[3] Height; weight; hip and waist circumferences

[4] Verify empty rectal vault prior to rectal biopsy procedure

[5] Phone or email contacts will include the following topics: compliance, adverse events, reminder to switch bottles, reminder to bring unused pills back to clinic. Participants will be contacted within 3 days after each biopsy visit (after Clinic Visits 2, 3, and 4), and at Weeks 1, 3, and 6 (± 3 days).

[6] Range: 8 weeks – 9 weeks and 2 days (56 – 65 days) after starting the study agent

[7] Range: 11 weeks – 12 weeks and 2 days (77 – 86 days) after starting the study agent

[8] If a participant comes off-agent (e.g. due to AE or concomitant medication), the Off-Agent Visit will be scheduled for as soon as possible after the participant stops the study agent.

[9] Urine samples will be obtained only from participants who agree to future unspecified research in the consent form.

[10] Clinic Visit 1-4: 1 green top tube for CMP and 1 purple top tube for CBC with differential. CMP and CBC will be processed on the day of the visit.

[11] 1 EDTA purple top tube for plasma, white blood cell (WBC), red blood cell (RBC); 1 red top tube for serum.

[12] ECOG performance status obtained at Screening Visit only. Vital signs include pulse, respirator rate, temperature, and blood pressure.

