7.2 Pre-study Evaluation

Clinic Visit 1: Screening

- Prior to the visit
 - The research staff will mail the participant a stool collection kit. The participant will collect stool and bring it to the clinic. Participants who fail to bring in the stool sample to the office visit will be asked to try to produce a sample during the clinic visit. If unable, they will be asked to bring or mail the stool sample after Clinic Visit 1 for the fecal occult test.
- During the visit
 - Obtain written informed consent (the study participant will keep a copy).
 - Review medical history, physical including vital signs, ECOG performance status, concomitant medications, and symptoms.
 - Obtain the following specimens:
 - One tube of urine (for optional future research)
 - One tube of stool (brought from home for fecal occult blood test)
 - Two tubes of blood (for clinical laboratory measurements): 1 green top for CMP and 1 purple top for CBC with differential.
 - Two tubes of blood (for research): 1 EDTA purple top for plasma, white blood cell (WBC), red blood cell (RBC); 1 red top for serum.
 - Perform a pregnancy test
- After the visit
 - Research staff will review final inclusion/exclusion criteria based on laboratory results.
 - Participant will be registered in the Northwestern Oncology Trial Information System (NOTIS).
 - Results of the inclusion/exclusion criteria review will be communicated to the participant.

Clinic Visit 2: Baseline

Within 6 weeks of Clinic Visit 1

- Prior to the visit
 - The research staff will mail or give the participant a stool collection kit. The participant will collect stool and bring it to the clinic.
 - The research staff will mail or give the participant the Food Frequency Questionnaire (FFQ) and Baseline Clinic Visit Questionnaire. The participant will complete these questionnaires prior to arriving.
- During the visit
 - Review vital signs, concomitant medications, and symptoms.
 - Physical exam may be performed when deemed appropriate by study team due to significant changes or medical events.
 - Review the FFQ and Baseline Clinic Visit Questionnaire.
 - Obtain the following specimens:
 - One tube of urine (for optional future research)

- One tube of stool (brought from home for fecal occult blood test)
- Two tubes of blood (for clinical laboratory measurements): 1 green top for CMP and 1 purple top for CBC with differential.

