13. STATISTICAL CONSIDERATIONS

13.1 Study Design/Description

This is a Phase IIa, 3 arm, randomized placebo-controlled trial (40 subjects in each of two treatment arms and 10 subjects in the placebo arm) to evaluate whether, use of aspirin at 325 mg in a three weeks on/three weeks off regimen has similar/equivalent efficacy. Our hypothesis is that intermittent use group will show equivalent reduction in the primary endpoint (proliferation: apoptosis ratio) and reduced risk of adverse events, as that using aspirin daily.

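### Section 13.5 does not limit the fecal occult blood comparison to post-dose tests, so a positive at the pre-dose baseline visit counts as an event in the plan's only between-arm safety test

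*Combined protocol and SAP*

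**What the plan says.** Section 13.1 hypothesises that the intermittent schedule carries "reduced risk of adverse events, as that using aspirin daily". Sections 1.2 and 13.5 list the fecal occult blood test as a secondary objective and label it a measure of adverse events.

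The analysis rule in 13.5 has two sentences. The first: "Fecal occult blood tests will be categorized as binary (present vs. absent) at each time visit". The second: "Proportion of patients with at least one positive test will be compared between arms using Fishers exact test". The reason given is that incidence is expected to be low. No alpha, sidedness, expected rate or power is stated for this test.

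On timing, section 8.2 says: "Fecal occult blood test will be used to monitor the safety of the treatment at each clinic visit". The schedule in 7.1 shows stool collection at all four clinic visits. Inclusion criterion 4.1.5 requires a negative test, and 7.2 places the eligibility review after Visit 1. Footnote 1 of 7.1 says: "Registration and randomization will occur between Clinic Visit 1 and Clinic Visit 2". At Visit 2 the participant brings stool collected at home, and study agent is dispensed at that same visit (5.2, 7.2).

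The toxicity rule, which is all of 13.7, reads: "All participants will be evaluable for toxicity from the time of their first dose of aspirin".

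**The concern.** A treatment-safety endpoint should count events that treatment could have caused. The Visit 2 stool is produced before the participant holds any capsules. Because the arm is already assigned by then and 13.5 takes any positive at any visit, a participant who bleeds before the first dose enters the comparison as an event in the assigned arm.

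No rule elsewhere clearly removes such a result. Eligibility is settled on the Visit 1 sample, and the withdrawal rule in 5.6 is framed for "Individuals who have one of the following results during the intervention".

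At stake is the sharpness of the one planned comparison that bears on the safety half of the hypothesis. Positives are expected to be rare, so a few that have nothing to do with the drug can mask a real difference. Leaving the definition open also means that someone may have to decide how to treat Visit 2 positives after seeing them.

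**Working it through.** **1. Which visits can contribute a positive**

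| Visit | Randomized? | Dosed? | Can add an event under 13.5 as worded? |
|---|---|---|---|
| 1 (screening) | No | No | No: 4.1.5 requires a negative test |
| 2 (baseline) | Yes | No | Yes |
| 3 (week 9) | Yes | Yes | Yes, as intended |
| 4 (week 12) or Off-Agent | Yes | Yes | Yes, as intended |

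Only Visit 2 is at issue.

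**2. The plan's own figure.** There is none for this test. The power of 0.81 in 13.4 concerns the primary equivalence test. It recomputes at 0.814 and does not bear on this point.

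**3. Inputs.** From the documents: 40 per aspirin arm (5.1, 13.1), or 32 after 20% dropout (13.4). Assumed, because the documents give no value: two-sided alpha of 0.05; a comparison of the two aspirin arms; post-dose positive rates p of 20%, 15% or 10% (daily) v 5% (intermittent); Visit 2 positivity b of 2%, 5% or 10%, equal in both arms and independent of later tests.

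**4. Expected number of Visit 2 positives in the two aspirin arms.** 80 × b = 1.6, 4 or 8 participants.

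**5. Observed rate when Visit 2 counts.** Observed rate = 1 − (1 − p)(1 − b). For a true 20% v 5% (ratio 4.0):

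- b = 2%: 1 − 0.80 × 0.98 = 21.6%; 1 − 0.95 × 0.98 = 6.9%; ratio 3.1
- b = 5%: 1 − 0.80 × 0.95 = 24.0%; 1 − 0.95 × 0.95 = 9.75%; ratio 2.5
- b = 10%: 1 − 0.80 × 0.90 = 28.0%; 1 − 0.95 × 0.90 = 14.5%; ratio 1.9

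**6. Power of Fisher's exact test.** Sum the product of the two binomial probabilities over every pair of counts with two-sided p at or below 0.05.

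| Post-dose rates, n per arm | b = 0 | 2% | 5% | 10% |
|---|---|---|---|---|
| 20% v 5%, n = 40 | 41% | 37% | 31% | 24% |
| 15% v 5%, n = 40 | 18% | 17% | 15% | 12% |
| 10% v 5%, n = 40 | 4% | 5% | 5% | 5% |
| 20% v 5%, n = 32 | 28% | 25% | 22% | 18% |

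**7. What one or two extra positives do, 40 v 40.** Suppose they fall in participants who are not positive later.

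- 6 v 0 (p = 0.026) becomes 7 v 1 (p = 0.057) with one added per arm, and 8 v 2 (p = 0.087) with two.
- 9 v 2 (p = 0.048) becomes 10 v 3 (p = 0.066).
- 8 v 1 (p = 0.029) becomes 9 v 2 (p = 0.048) and stays below 0.05.

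**8. False positives.** With equal post-dose rates of 5%, the rejection rate at n = 40 is 0.4% at b = 0 and 2.5% at b = 10%. It stays below the nominal 5%.

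**The case against.** The strongest reply is that the plan already signals the intended window. Section 11.1.1 makes adverse events reportable only once consent is signed and baseline assessments are complete, and Visit 2 is the baseline visit. Section 13.7 starts toxicity at the first dose. Section 8.2 describes the test as monitoring the treatment, and there is no treatment before Visit 2. This stands as evidence of intent. But those sections govern adverse-event recording and toxicity evaluability. None of them redefines the 13.5 endpoint, and 8.2 itself refers to every clinic visit.

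The second reply is that the effect may be small, and this also stands. Participants tested negative at most six weeks before Visit 2. Users of NSAIDs and anticoagulants are excluded, as is anyone with a history of anemia, ulcer or gastrointestinal bleeding. The true Visit 2 rate could be near zero. The test is an unpowered secondary comparison, and primary inference is untouched.

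Three stronger readings are tempting, and the documents do not support them:

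- *Section 13 compares no adverse events by arm.* It does: 13.5 itself calls a positive occult blood test an adverse event and compares it between arms.
- *The placebo arm has no safety data, because 13.7 starts at a dose of aspirin.* The 10 placebo participants never take aspirin, so the wording does not fit them. Section 11.1.1 nevertheless records all adverse events whether or not related to study agent, and 13.8 uses the broader term. This is a drafting slip that loses no data.
- *The absence of a planned by-arm table of other adverse events or laboratory values is an error.* Apart from occult blood, section 13 lists no by-arm summary of reported events. Such a table is routine reporting, and the Data and Safety Monitoring Plan and the Data Management Plan, which may cover it, are on file but not in the documents reviewed.

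**Conclusion.** The point holds as a minor gap in an endpoint definition. Followed as written, 13.5 counts a pre-dose positive; other sections suggest that this was not intended.

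A reader might infer that the comparison is biased toward one schedule. It is not. The Visit 2 sample follows blinded randomization and precedes any drug, so extra positives are equally likely in each arm. They pull the contrast toward no difference, which works against the trial's safety hypothesis and does not flatter it.

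The size depends entirely on rates that the documents do not give. The loss is noticeable only if the post-dose contrast is large and Visit 2 positives occur: for 20% v 5%, 4 to 17 percentage points of power at 40 per arm. At 10% v 5% the test has almost no power either way, although the observed ratio would still shrink from 2.0 to between 1.7 (11.8% v 6.9%) and 1.3 (19.0% v 14.5%). The near-threshold examples in step 7 show that a result can cross 0.05, not that it is likely to.

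**What to change.** In 13.5, define the event: *a participant counts as positive if any occult blood test after the first dose of study agent (Visit 3, Visit 4 or Off-Agent Visit) is positive; Visit 2 results are tabulated by arm as baseline.*

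In 13.7, as an accompanying wording correction, replace the first dose of aspirin with the first dose of study agent, so that the sentence covers the placebo arm.

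A descriptive table of reported adverse events by arm is advisable as ordinary reporting.

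Both edits use data already collected and need no new samples, visits or staff. They should be made before unblinding. One limit remains: a participant positive at Visit 2 and again after dosing still counts, so bleeding unrelated to the drug is not fully removed. The baseline tabulation will show how often that arises.
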